1.1 P3 EQUATE Overview

The P³OPPY Project is one of five projects within the P3 EQUATE Network. The overarching goal of the P3 EQUATE American Heart Association Health Equity Research Network (HERN) is to promote equity in Maternal and Infant Health outcomes by identifying innovative and cost-effective strategies to enhance access to quality health information, care, and experiences during pregnancy, postnatal and postpartum/preconception periods, particularly for Black and underserved populations. Collectively, our team will collaborate with pregnant and postpartum people and their families, hospitals, and communities to discover ways to reduce racism and social problems that contribute to poor health outcomes.

1.2 P³OPPY Overview

The purpose of the P3 Providing an Optimized and emPowered Pregnancy for You (P³OPPY) study is to evaluate promising interventions to reduce disparities and improve healthcare access and quality among pregnant women and their infants from historically marginalized communities. We will test the hypothesis that an innovative mobile-health integrated care model and/or a community health worker integrated care model will improve pregnancy outcomes among women who experience persistent disparities. POPPY has three aims: 1) Qualitative aim to understand how best to tailor the digital health and community health worker interventions (this is addressed in a separate, previously approved IRB application), 2) a pilot randomized trial (n=40) randomizing eligible patients to a digital health intervention, a community health worker intervention, or both (covered in the enclosed application), 3) a randomized trial of 400 pregnant patients to determine if digital health and/or community health workers can improve pregnancy outcomes (a future application). The enclosed protocol describes the activities of Aim 2, the pilot trial.

1.3 Study Abstract

US maternal mortality and preterm birth rates are among the highest in the developed world due, at least in part, to a combination of racial, regional and socioeconomic disparities. Our preliminary work demonstrates that differences in the Area Deprivation Index (ADI) are associated with racial/ethnic disparities in maternal and perinatal outcomes in Alabama. Patients living in resource-poor, or high ADI areas, may benefit from modifications at the patient-level to ensure equitable access to high-quality maternal care. The enclosed P³OPPY Pilot Study will determine if randomizing and implementing a digital health and/or community health worker interventions are feasible.

1.4 Pilot Study Aims

1. To assess the feasibility of the DHI and CHW interventions by assessing patient acceptance and use of the intervention.
2. To assess study enrollment to determine appropriateness and usefulness of the inclusion and exclusion criteria to estimate enrollment duration in the planned trial.
3. To determine the number of prenatal visits and the incidence of some of the maternal and neonatal outcomes (ones with higher prevalence) or surrogate outcomes that will be targeted in the planned factorial design randomized controlled trial. (Data will be collected on all relevant maternal and neonatal outcomes. The randomized feasibility design will allow for effect size estimates of the intervention on the incidence of maternal and neonatal outcomes, which will aid in determining the appropriate target outcomes as well as power calculation of the more definitive trial.)

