1.5 Purpose of Study Protocol

The purpose of the P3 Providing an Optimized and empowered Pregnancy for You (P³OPPY) study is to evaluate promising interventions to reduce disparities and improve healthcare access and quality among

pregnant women and their infants from historically marginalized communities. The enclosed protocol for the pilot study will assess feasibility of randomization and implementation ahead of the planned clinical trial.

A manual of operations supplements the protocol with detailed specifications of the study procedures.

2. Background

Maternal health disparities in the United States (US) are disturbingly high — The US has the highest maternal mortality (MM) rate – 32.9 deaths per 100,000 live births – among industrialized countries, and Alabama has the third highest MM rate in the US [1,2](#). These starkly high rates are marked by persistent, unacceptable disparities. Unfavorable social determinants of health (SDoH), structural racism, and systemic barriers lead to suboptimal health outcomes in pregnant women from historically marginalized backgrounds [3,4](#). In 2020, the MM rate for Non-Hispanic White (NHW) women in the US was 19.1 deaths per 100,000 births, while the MM rate for NHB women was nearly three times higher at 55.3 deaths per 100,000 live births.¹ MM represents the “tip of the iceberg,” as each death represents numerous “near-misses” that the Centers for Disease Control and Prevention (CDC) captures in a severe maternal morbidity (SMM) composite of 21 outcomes that have profound short and long-term ramifications [5,6](#). As summarized in a review by [name] (P3OPPY Co-PI), NHB women are also more likely to experience each component of the CDC SMM index versus NHW women [7](#).

Our NIH-funded supplement (3UL1TR003096) on racial disparities in maternal mortality identified a significant linear relationship between increasing levels of area deprivation and increased SMM/MM ($p<0.01$)

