4.2 Design Summary

We will challenge existing care paradigms by testing the effectiveness of integrating innovative platforms into the existing healthcare system, including existing DHI and CHW programs from within our consortium, to eliminate critical barriers to equitable healthcare access. After seeking input from a Community Advisory Board, these interventions will be refined and deployed for pilot testing. We will specifically include NHB communities at the highest risk of adverse pregnancy outcomes and which were historically underrepresented in clinical research due to structural racism. Our cross-disciplinary collaboration effectively employs experts across the community, maternal, and infant health continuum. The use of community-based participatory research to tailor the digital health platform and optimize CHW activities/interactions represents a paradigm shift in pregnancy care. Novel technological innovations include the use of secure educational messaging and connection to local resources.

For this pilot, we will randomize a total of 40 eligible participants, 10 to usual care, 10 to DHI, 10 to CHW, and 10 to DHI + CHW

4.3 Eligibility Criteria:

Inclusion Criteria:

- Self Identifies as NHB
- Between 16-49 years old
- 8⁰ - 22⁶ weeks gestational age with a live fetus
- Dating sonogram at <23 weeks gestation
- ADI National 4th or 5th Quintile
- Planning to deliver at UAB Hospital
- Speaks and writes in English
- No indication for delivery at the time of enrollment
- Viable singleton or dichorionic twins

Exclusion Criteria:

- Declines Randomization
- Speaks or writes in languages other than English
- Currently incarcerated
- Fetal demise diagnosed prior to enrollment
- Known major structural chromosomal abnormalities prior to enrollment

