5.2 Recruitment and Randomization

All pregnant patients <23 weeks' gestation will be screened for eligibility. The screening will occur in the inpatient and outpatient settings at UAB. In the inpatient setting, patients with limited or no prenatal care frequently present to the obstetric triage unit and/or to the emergency department for pregnancy care, yet this often does not translate to routine prenatal care leading researchers to conclude that these patients are "vulnerable" and "should be considered as a public health strategy worth investigating" [32, 33](#). The OB/GYN team is consulted on all obstetric patients in the ED and obstetric triage unit and a "New OB Lab Panel" is ordered by routine. If this panel is ordered in the ED or obstetric triage unit, a page will be sent to the CWRH research team (on-site 24/7), alerting them to screen the patient for P³OPPY. Additionally, the CWRH team will screen the clinic schedules for potentially eligible prenatal patients in outpatient obstetric clinics. Potential participants will then be approached for enrollment by a trained member of the CWRH team.

The 1:1:1:1 randomization sequence will be uploaded by [name], the Data Coordinating Center lead. Study team will be blinded to the randomization sequence.

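### Does Aim 3's prenatal-visit count need a stated window, visit type and denominator before the pilot can use it?

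*Combined protocol and SAP*

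**What the plan says.** Section 1.4, Aim 3, opens "To determine the number of prenatal visits and the incidence of some of the maternal and neonatal outcomes (ones with higher prevalence". This is the only place where the visit count is named as an outcome. The same aim then explains what randomisation is for: "The randomized feasibility design will allow for effect size estimates of the intervention on the incidence of maternal and neonatal outcomes". That sentence, which leads on to planning the larger trial, concerns clinical outcomes and does not mention visits.

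Section 4.3 admits women at 8w0d to 22w6d "weeks gestational age with a live fetus", and also requires "Viable singleton or dichorionic twins". Section 5.2 recruits from outpatient clinics, the emergency department and obstetric triage. It observes that "patients with limited or no prenatal care frequently present to the obstetric triage unit and/or to the emergency department for pregnancy care". It treats this contact as distinct from regular clinic follow-up, remarking "yet this often does not translate to routine prenatal care". On allocation it says "The 1:1:1:1 randomization sequence will be uploaded by" the Data Coordinating Center lead.

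On detail held elsewhere, section 1.5 states "A manual of operations supplements the protocol with detailed specifications of the study procedures", and section 7.2 places the detailed data collection forms in a manual of procedures. The assessment table in the In-person Visit / Procedures section lists a prenatal-course item at 28 to 32 weeks and a labour and delivery form that covers the prenatal course. That section also plans a medical record release.

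**The concern.** A visit count depends on how long a woman is observed and on what is counted. The protocol text fixes neither, and three readings give different numbers.

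- **From enrolment:** early entrants have more time to accumulate visits.
- **Whole pregnancy:** the count includes visits before randomisation, which the interventions cannot affect, in a sample that mixes clinic patients with women who may have had little earlier care.
- **Visit type:** the digital-intervention section tells participants with concerns to call the clinic or come to the MEU (an abbreviation the protocol does not expand). If MEU encounters counted as prenatal visits, the digital arms could show more visits with routine attendance unchanged.

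Under either window, earlier delivery also lowers the count. The interventions offer reminders, transport and a community health worker at visits, so a reader will want to treat the count as attendance and may carry it into the planned 400-patient trial. If the definition is loose, that reading could mislead.

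**Working it through.** There is no plan figure to reproduce: section 6 gives a convenience sample of 40 (4 × 10) with no calculation based on visits. The checks are how large the ambiguity is, and whether the text leaves the meaning open.

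**Observation time from enrolment** (entry limits from section 4.3; delivery at 40 weeks assumed): 40 − 8 = 32.0 weeks; 40 − 22w6d = 17.1 weeks.

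**Expected visits.** The documents give no visit schedule. Assume visits at weeks 8, 12, 16, 20, 24 and 28, then every 2 or 3 weeks to about 36, then weekly.

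| Visits after entry | 2-week step | 3-week step |
|---|---|---|
| Entry 8w0d, delivery 38 weeks | 11 | 9 |
| Entry 22w6d, delivery 38 weeks | 8 | 6 |
| Entry 8w0d, delivery 39 weeks | 12 | 10 |
| Entry 8w0d, delivery 36 weeks | 9 | 7 |

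The extremes of entry differ by 3 visits, and so do deliveries at 36 and 39 weeks. A constant rate of 0.25 to 0.5 visits per week would widen the entry gap to 8.0 v 4.3, or 16.0 v 8.6, but it ignores the sparser early schedule assumed above.

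**Chance imbalance between arms** (uniform entry assumed): SD of entry week = 14.86/√12 = 4.29 weeks. For 10 v 10, the SD of the difference in means = 4.29 × √(2/10) = 1.92 weeks, with a 30% chance of a gap of 2 weeks or more. For 20 v 20 it is 4.29 × √(2/20) = 1.36 weeks, with a 14% chance.

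**Effect of that imbalance.** A simulation over 384 sets of assumed inputs used both grids, attendance of 70% or 80%, and a range of entry patterns, delivery spreads and between-woman variation. The count fell by 0.16 to 0.21 visits per week of later entry. A 2-week gap therefore moves the mean by 0.32 to 0.42 visits, against a 10 v 10 standard error of 0.66 to 1.79.

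**Gain from adjusting for entry week.** R² of the count on entry week was 0.015 to 0.265, median 0.056. The covariate costs about 1/(40 − 4 − 2) = 2.9% of variance.

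- Median: √(0.944 × 1.029) = 0.986, so the standard error shrinks by about 1.4%.
- Best case: √(0.735 × 1.029) = 0.870, a 13% reduction.
- Worst case: √(0.985 × 1.029) = 1.007, slightly worse than no adjustment. R² fell below the 2.9% cost in 12% of sets.

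**Unscheduled encounters.** One counted encounter per woman equals 1/11 = 9% to 1/6 = 17% of expected visits. The documents give no encounter rate, so the one is hypothetical.

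**What the text implies about visit type.** Section 5.2 contrasts triage and emergency presentation with routine prenatal care. The community health worker section speaks of accompanying women to prenatal visits and to a doctor's appointment. The background cites missed prenatal-care appointments. All three point to clinic prenatal visits. Inflation through the MEU needs the opposite reading, and the message in question also offers a call to the clinic.

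**The case for a change.** The strongest case for a change rests on what happens after randomisation. Entry week and earlier care are balanced in expectation. Delivery timing and MEU visits are not protected in this way, since the interventions could affect both. Determining the visit number is a stated aim, and fixing the definition before outcomes are seen would prevent a choice made afterwards. The programme's own earlier evidence is on missed appointments, which an undefined count cannot be set against. The manuals are promised for procedures and forms, not expressly for outcome definitions.

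Much of this stands as a caution in interpretation. The protocol text does not define the count, a higher or lower number should not be read as better or worse attendance, and delivery timing belongs beside it. But the protocol makes no attendance claim and promises no arm comparison of visits, so the post-randomisation routes distort nothing that is planned. If the larger trial adopts another definition, visits could be recounted from the medical records, within the limits of incomplete outside records.

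The more elaborate remedies are not clearly better. A ratio of attended to expected visits needs a schedule the documents do not contain, conditions on delivery (itself post-randomisation), is unstable after early loss, and suits twins poorly. A count from randomisation to delivery would still depend on entry week and delivery timing.

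**Conclusion.** No change follows. This is missing detail that a competent analyst would fill sensibly by counting clinic prenatal visits from the records, stating the window used, and giving gestational age at entry and delivery alongside. Entry timing is worth 3 expected visits between the extremes on the assumed grids. Between arms it is noise: a 2-week imbalance moves the mean by 0.32 to 0.42 visits, and adjusting for it typically shortens the standard error by about 1.4%, for a comparison that is not planned. Those sizes rest on assumed schedules, delivery dates and attendance.

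The conclusion itself rests on the text: a descriptive feasibility count, no stated figure or test that depends on it, surrounding wording that points to clinic appointments, and form-level detail deferred to manuals not seen here. It would need revisiting if the count became a comparative endpoint or an input to the larger trial's sample size.

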1.5 Purpose of Study Protocol

The purpose of the P3 Providing an Optimized and empowered Pregnancy for You (P³OPPY) study is to evaluate promising interventions to reduce disparities and improve healthcare access and quality among

pregnant women and their infants from historically marginalized communities. The enclosed protocol for the pilot study will assess feasibility of randomization and implementation ahead of the planned clinical trial.

A manual of operations supplements the protocol with detailed specifications of the study procedures.

2. Background

Maternal health disparities in the United States (US) are disturbingly high — The US has the highest maternal mortality (MM) rate – 32.9 deaths per 100,000 live births – among industrialized countries, and Alabama has the third highest MM rate in the US [1,2](#). These starkly high rates are marked by persistent, unacceptable disparities. Unfavorable social determinants of health (SDoH), structural racism, and systemic barriers lead to suboptimal health outcomes in pregnant women from historically marginalized backgrounds [3,4](#). In 2020, the MM rate for Non-Hispanic White (NHW) women in the US was 19.1 deaths per 100,000 births, while the MM rate for NHB women was nearly three times higher at 55.3 deaths per 100,000 live births.¹ MM represents the “tip of the iceberg,” as each death represents numerous “near-misses” that the Centers for Disease Control and Prevention (CDC) captures in a severe maternal morbidity (SMM) composite of 21 outcomes that have profound short and long-term ramifications [5,6](#). As summarized in a review by [name] (P3OPPY Co-PI), NHB women are also more likely to experience each component of the CDC SMM index versus NHW women [7](#).

Our NIH-funded supplement (3UL1TR003096) on racial disparities in maternal mortality identified a significant linear relationship between increasing levels of area deprivation and increased SMM/MM ($p<0.01$)

The effect was significant in the top three (most deprived) area deprivation index (ADI) quintiles. The ADI quantifies socioeconomic conditions linked to individual health outcomes [8](#). The ADI scale ranges from 0 – 100; 0 represents abundant resources and 100 represents the most impoverished community. Alabama patients residing in high-deprivation communities, defined as the 5th highest ADI quintile (Q), had 78% greater odds of SMM/MM compared to patients living in resourced communities (defined as ADI Q1) (OR, 1.78; 95% Confidence Interval (CI), 1.22 – 2.59; $p=0.003$) (Table 1). Other factors including NHB race, age ≥ 35 years, residing in medically underserved areas and having Medicaid or Medicare insurance were also significantly associated with an increase in SMM/MM (under review for publication). Qualitative stakeholder interviews ($n=20$) conducted by our team identified several themes felt to contribute to persistent disparities in Alabama, including the legacy of racism, institutional distrust, lack of racial diversity in medical providers, poverty, lack of transportation and other needed infrastructure [9](#).

Table 1. Association Between ADI, Race, and SMM / MM Among Women Delivering at UAB Hospital 2010 – 2020

[figure not shown]
Variables	Adjusted OR* (95% CI)	P-value
Area deprivation index (quintiles)		
1 st Quintile	1.00	
2 nd Quintile	1.18 (0.95-1.47)	0.143
3 rd Quintile	1.47 (1.18-1.84)	0.001
4 th Quintile	1.55 (1.18-2.04)	0.002
5 th Quintile	1.78 (1.22-2.59)	0.003
Race		
NHW	1.00	
NHB	1.81 (1.42-2.30)	<.001
Hispanic/Latino	0.84 (0.58-1.23)	0.369

*Odds ratio and 95% confidence intervals computed using Genmod procedure with repeated subject = census block group geoid to adjust for within-subject correlation.

Inequalities in infant outcomes are equally egregious — Infant mortality rates (IMR) in the US are also among the highest in the developed world due largely to a combination of higher gestational age (GA)-specific mortality among term infants and higher rates of preterm birth (PTB) [10](#). We identified significant disparities in IMR and other adverse infant outcomes according to race [11](#) and socioeconomic status (SES) [12](#) in the US and Alabama. Alabama’s IMR was 9.3/1000 births in 2016, and despite improving to 7.0/1000 in 2018, it remains significantly above the national IMR of 5.8/1000 and among the highest in the US. Our analysis of national data showed that inter-state IMR variation is highly correlated with rates of extremely PTB ($r^2 = 0.71$; $p<0.001$) that are closely related to the proportion of births to NHB women [13](#).

In an ecological study of 6,901,328 US infants born in 2017-2018, we demonstrated that privately insured infants had a 30% lower IMR compared with Medicaid-insured infants after adjustment for race, sex, multiple births, and maternal pregnancy risk factors [14](#). Privately insured mothers had higher rates of first trimester prenatal care (PNC) (85.6% vs. 66.6%; $p<0.001$) and lower rates of infant morbidity, preterm births (PTB) and low birth weight (all $p<0.001$). Furthermore, Medicaid Enhanced PNC Programs are associated with lower IMR suggesting that interventions that enhance maternal pregnancy care improve infant outcomes [15](#).

In a recent study of 4 neonatal intensive care units by [name] (Co-I), NHB infants <29 weeks' gestation lived in areas with higher ADI percentiles than similar NHW preterm infants [16](#)[16](#). Specifically, extremely preterm infants at UAB were more likely to be NHB and had a high median ADI (81, IQR 64-92) scores. There was a significant association between ADI and mortality after adjustment for baseline characteristics. Findings from the Jefferson County, AL Health Equity Team, led by [name] (Co-I), align with [name]' findings (Figure 1) [17](#)[17](#). SDoH including racism and SES remain important independent risk factors for adverse infant outcomes.

to

Digital health interventions (DHI) are promising channels to support improved outcomes in under-resourced communities — Though COVID-19 exacerbated the many challenges facing maternal and child healthcare delivery, it simultaneously provided opportunities to redesign the delivery of care [18](#). One such opportunity is the use of the DHI short message service (SMS) which the Cochrane Review has shown to be a promising strategy for improving maternal, newborn, and child health [19](#). Although some studies show mixed results for text-based DHI interventions in low- and middle-income countries (LMIC) and high-income countries, others targeting pregnant and postpartum (PP) women have shown these interventions improved exclusive breastfeeding, increased PNC, and increased skilled attendants at birth where a lack of skilled attendants is common [20](#). While many patients receiving texts felt supported by DHI, others cited lack of network access, internet, or phone, and literacy or privacy issues as concerns [21](#).

[figure not shown]
One of our EQUATE Partners, [name] (P³OPPY Consultant), Chief Innovation Officer at Penn Medicine, in conjunction with Memora Health, developed a text-based DHI for maternal and newborn care that does not rely on a data plan or smartphone [22](#)[23](#). The DHI primarily works in two ways, 1) sending time-sensitive, culturally relevant educational texts and 2) replying to patients' texts regarding medical concerns with artificial intelligence-driven algorithms. Since smartphones nor internet access are needed for text-based solutions, this is a potentially sustainable and scalable intervention. However, DHI solutions, while helpful, may not be able to replicate the in-person face-to-face support during pregnancy and PP. Thus, CHW will also be tested in our factorial design trial.

Community health workers (CHW) comprise another promising, sustainable, and scalable strategy to improve maternal and child outcomes in under-resourced areas — There is substantial evidence supporting the effectiveness of integrating CHWs into the clinical care team [24](#)[24](#). A 2022 systematic review investigating CHW interventions and maternal/child health concluded that CHW improved pregnancy and infant health knowledge, increased PNC, and reduced IMR in LMIC [25](#). CHWs are also known to both increase access to services and improve the quality of culturally competent care. In fact, the Community Preventive Services Task Force recommends using CHW based on multiple studies demonstrating reductions in health disparities (particularly related to cardiovascular disease (CVD) and the cost-effectiveness of CHW use [26](#)[26](#). Despite this, there is limited data on the integration of CHW in the US as part of a strategy to reduce racial disparities in maternal/child health. Preliminary data from the Connection Health CHW Program, from which the P³OPPY CHW program will be adapted, demonstrated that pregnant patients paired with a CHW had 100% smoking cessation and 77% fewer missed PNC appointments than SES-matched pregnant patients without a CHW.

Community-based participatory research (CBPR) is a powerful strategy harnessing community partnerships at each stage of research — CBPR, an innovative research methodology that treats community members as equals in the research team [27](#), has transformative potential to improve maternal/infant health outcomes. In our previously mentioned qualitative interviews, stakeholders cited distrust of the medical system as a contributing factor in racial disparities in maternal death. The P³OPPY

Project provides an opportunity to mitigate this distrust through meaningful partnership. Our team ([name], Co-I and [name], EQUATE Core) has extensive expertise in CBPR in the Deep South and other resource limited settings [28-30](#).

A properly designed randomized controlled trial (RCT) grounded in a CBPR framework³¹ is urgently needed to investigate promising DHI and CHW interventions to reduce the disparities outlined above. As shown in Figure 2, our conceptual model identifies multi-level contributors to racial disparities in maternal/infant outcomes. Each of the two P3OPPY interventions has the potential to target various disparities in the EQUATE conceptual model. The proposed aims align with the overarching goal of the American Heart Association Health Equity Research Network on Disparities in Maternal-Infant Outcomes to “aggressively address SDoH while working to improve health equity for all communities.”

3. Preliminary Data from Qualitative Interviews from AIM 1

What follows in this section 3 is a brief summary of recommendations from our one-on-one semi-structured virtual interviews from Aim 1 occurring from November 2022 – January 2023 from community leaders and maternal child health service providers for community health worker programs and digital health interventions. Note that these data are preliminary and do not include findings from ongoing interviews.

Interested parties were defined as clinical and alternative providers who provide health services to pregnant, laboring, and postpartum people and infants who identify as Black or African American in Alabama. Other interested parties were community leaders who work or volunteer with communities who primarily identify as Black or African American in Alabama. These included leaders of community-based organizations, faith-based leaders, educators, etc. outside of direct services in maternal and child health. Focus was initially on Jefferson County, but we were inclusive of perspectives outside of the county to promote feasibility in scaling up the future pilot.

Community Health Worker Intervention Recommendations:

- Characteristics of CHW:
 - Emphasize these qualities as part of recruitment, hiring interview, and screening to match clients to CHWs.
 - Seek CHWs with the following:
 - Qualities: Flexible, engaging, nonjudgmental, trustworthy, empathetic, charismatic, perceptive, approachable, respectful
 - Skills: strong listening and communication, perceptive, professional, knowledgeable, educator, advocate, proactive, resourceful
 - Demographic Characteristics: look like the participant/ relatable (i.e. mom, same race, similar background and/or from similar geographic area)
- Training for CHW:
 - Training should include: content specific to pregnancy, postpartum maternal and infant care; difficult conversations, intrinsic bias training, leadership training, art therapy, active listening, and educational program to overcome loneliness offered by UAB chaplain group.
 - Have staff listen to questions from clients about current events, new research; staff read a study and report main points to the rest of the staff.
 - Set up brief meetings with local organizations around Birmingham so the staff know the resources and exact point of contact. Have a running list and practice the “warm handoff” connection to services.
- Connecting to Moms:
 - Communicating to General Community:
 - What? Promote and inform about the role, duties, and generally who a CHW is in general and within this context.
 - Who? Communicate with local leaders (informal and formal), pregnant people, and young families.
 - Where? At existing community events (i.e. health screenings, schools, continued communication at health department, Parent Teach Organizations, or other places community members frequent.
 - Pre-Meeting: Screen centrally to match clients to CHWs based on similar characteristics when possible.
 - First Meeting:
 - Meet in-hospital or clinic.

- Have centralized screener introduce CHW to client via phone and let them decide where to meet initially. Locations: in client's home or other nearby community gathering place- church, community center, restaurant, etc.
- Other Visits: Meet where client is comfortable. Ideally the phone calls initiated by the CHW will encourage the client to initiate communication to CHW too! Over time, a relationship will be natural and meeting at home may become easier and more comfortable. Incentivize the program to encourage update. Incentives may include care items for infants (formula, clothes, diapers, etc.) and partnering with corporations may offset these expenses.
- Role and Duties:
 - Provide specific, inclusive description to clients, communities, and leaders.
 - Examples: Advocate for clients (prep client before an appointment to advocate for them self, attend appointments with them to advocate), answer questions about health, improve health literacy, remind and support in scheduling, securing childcare/ transportation for appointments, home visits for blood pressure other screenings like mental health issues; Communicate to avoid loneliness and isolation; Educate about nutrition, sleep, care for clients and infants, when to seek medical care vs. basic home care, connect to existing resources to meet all of family's needs not just direct infant and maternal health services.
- Timing/ Availability:
 - Set clear expectations during recruitment/ hiring for CHW to "meet client where they are". This should include early evenings and weekends when clients may need to talk or have questions answered.
 - CHW should set and communicate with clients their clear expectations about their availability and what constitutes an emergency vs. nonemergency.
 - Visit/ communication frequency should change over time with more frequent communication in the first 6 weeks versus more spaced out over time during the remaining months.
- Concerns:
 - Confidentiality:
 - Communicate with clients and communities about the role, duties, and benefits of CHWs.
 - Clearly describe the training they receive and what information they are expected to keep confidential (i.e. not share with others in the community).
 - Consider using the example of provider/ patient confidentiality from the medical model (HIPAA) as some may be familiar with that.
 - Communicate clearly what they are required to report vs. the purpose they are there for.
 - Safety for CHW at in-home visits
 - Hire people from similar communities.
 - Set and communicate boundaries on visiting (times, days, and expectations for reporting so other members of the household are well-informed too.)

Digital Health Interventions:

- Mode:
 - Use text messages if possible. Varied opinions on whether a text link to a secured app would be a deterrent to use.
 - Use option to "opt in" to avoid the feeling that it is invasive.
- Interventionists/ facilitators:
 - Have a live person available to respond to questions about the messages. When they need to be available will vary widely.

- Avoid having to press 1 for this and press 2 for that phone trees that may feel complicated and inhuman. Avoid “BOT” response when possible to promote tailored responses and health literacy.
 - Increase message acceptability with messages from a known person or ability to respond to a known person (like a CHW or other trusted source) rather than mass automated messages.
 - Have a person on the team who is interested in social media to be ahead of trends and increase user-friendliness.
- Frequency/ timing:
 - Preferences for when the messages should be delivered varied.
 - Frequency should change over time with more depending on the stage of pregnancy or postpartum (i.e. more in the first 6 weeks then fewer over time. Some suggested once per week then once per month.)
 - Avoid overwhelming people with too many messages (risk they will ignore).
- Content of messages:
 - Messages should extend to current events and topics of interests for clients during their stage of pregnancy, delivery, and postpartum (i.e. move beyond providing info about vitamins during pregnancy).
 - Have programmed messages with flexibility. Call upon content/ social media experts to create anticipate questions/ identify current events to develop and send messages to respond to timely questions.
- Participant Access to Phone/ Data:
 - Interventionists should be flexible and understanding regarding access. A client’s phone number may change. They may have limit on number of minutes or limited knowledge of device/ app features. They may share a phone with a member of the household. They may lack data or consistent WIFI and require going to a community place with WIFI.
 - Be proactive in communicating frequently and work with community (family, neighbors, and faith-based leaders) to track down people’s new numbers and find places nearby where they can access WIFI for free. Work with different generations in a household or community to problem solve.
- Confidentiality concerns:
 - Be aware of community concerns regarding existing programs for free/ reduced costs device or data plans. Concerns of being tracked by the government and at risk of losing their social service benefits.
 - Be aware about device/ data access issues and sharing (noted above).
 - Utilize CHW as a bridge to health system and digital health information.
 - Frame concerns around DHI confidentiality using examples from other telehealth or in-person health (i.e. CVS pharmacy script reminder to pick up, patient portal with provider’s office, are bound by HIPAA (explain HIPAA) and at risk of breach).

4. Study Design

